13.1 Definitions

Term	Definition		
Adverse Event (AE)	Any untoward medical occurrence in a participant or clinical study participant administered an intervention which are not necessarily caused by or related to the Zippy's Friends programme.		
Serious Adverse Event	Any adverse event that -		
(SAE)	Results in death		
	 Is life-threatening* 		
	 Required hospitalisation or prolongation of existing hospitalisation** 		
	Results in persistent or significant disability or incapacity		
	Consists of a congenital anomaly or birth defect		
	 Other medically important condition*** 		

*Note: The term 'life-threatening' in the definition of serious refers to an event in which the study participant was at risk of death at the time of the event or it is suspected that used or continued used of the product would result in the participants death; it does not refer to an event which hypothetically might have caused death if it were more severe.

**** Note:** Hospitalisation is defined as an inpatient admission, regardless of the length of stay, even if the hospitalisation is a precautionary measure for continued observation. Pre-planned hospitalisation e.g. for pre-existing conditions which have not worsened, or elective procedures, does not constitute an SAE.

******* Note: other events that may not result in death, are not life-threatening, or do not require hospitalisation, may be considered as an SAE when, based upon appropriate medical judgement, the event may jeopardise the participant and may require medical or surgical intervention to prevent one of the outcomes listed above.

13.2 Causality

The assessment of whether or not an SAE is a consequence of receiving the intervention will be provided by the CI.

Relationship	Description	Reasonable possibility	
		that the SAE may have	
		been caused by the	
		intervention?	
Unrelated	There is no evidence of any causal relationship with the	No	
	intervention		
Unlikely	There is little evidence to suggest there is a causal	No	
	relationship with the intervention (e.g. the event did		
	not occur within a reasonable time after administration		
	of the study medication). There is another reasonable		
	explanation for the event (e.g. the participant's clinical		
	condition, other concomitant treatment).		
Possible	There is some evidence to suggest a causal relationship	Yes	
	with the intervention (e.g. because the event occurs		
	within a reasonable time after administration of the		
	study medication). However, the influence of other		
	factors may have contributed to the event (e.g. the		
	participant's clinical condition, other concomitant		
	treatments).		
Probable	There is evidence to suggest a causal relationship and	Yes	
	the influence of other factors is unlikely.		
Definite	There is clear evidence to suggest a causal relationship	Yes	
	and other possible contributing factors can be ruled		
	out.		

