In the unlikely event that any SAEs related to the intervention or research procedures should occur, the CI is responsible for ensuring that all site staff involved in this study are familiar with the content of this section. All SAEs must be reported immediately (and within 24 hours of knowledge of the event) to the study team. SAEs will be assessed at all follow-up time points, and intervention delivery staff will be trained to report these directly to the study team at any point during the study. Rates of SAEs by study arm will be reported to the SSC, and if required, to the REC. Additional information about the potential harm of the intervention will be collected through qualitative interviews with all stakeholders. Interventions such as Zippy's Friends may have side effects for participants or for the classroom as a whole. This will be investigated in the light of any reports.

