13.3 Reporting procedures

Any queries concerning adverse event reporting should be directed to the Study Manager

All SAEs, whether expected or not, should be recorded on the relevant report form and followed up to resolution wherever possible. The CI (or delegated member of the SMG) should sign and date the SAE reporting form to acknowledge that he/she has performed the seriousness and causality

assessments. SAEs should be reported from time of signature of informed consent, throughout the treatment period.

An SAE form is not considered as complete unless the following details are provided:

- Full participant study number
- A Serious Adverse Event
- A completed assessment of the seriousness, and causality as performed by the CI (or another appropriately medically qualified doctor registered on the delegation log).
- Only reports of related and unexpected SAEs should be submitted to the REC. These should be sent within 15 days of the CI becoming aware of the event.

14 Statistical considerations

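### The safety section covers SAEs from research procedures, but the causality scale grades only against the intervention, so a procedure-caused SAE would not qualify for individual REC reporting

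*Protocol*

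**What the plan says.** Three parts of the protocol's safety section bear on this.

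- **Section 13 (Safety reporting), opening paragraph.** The scope has two sources of harm: "In the unlikely event that any SAEs related to the intervention or research procedures should occur". Capture is not restricted by cause: "All SAEs must be reported immediately (and within 24 hours of knowledge of the event) to the study team". There is also an aggregate route: "Rates of SAEs by study arm will be reported to the SSC, and if required, to the REC".
- **Section 13.2 (Causality).** The question put to the chief investigator (CI) has one object: "The assessment of whether or not an SAE is a consequence of receiving the intervention will be provided by the CI". The lowest grade begins "There is no evidence of any causal relationship with the" and ends with the intervention. The column that turns grades into Yes or No asks only whether the intervention may have caused the event. Two descriptions give examples that refer to a study medication, which this trial does not have.
- **Section 13.3 (Reporting procedures).** Collection starts at consent: "SAEs should be reported from time of signature of informed consent, throughout the treatment period". The filter for individual reports is: "Only reports of related and unexpected SAEs should be submitted to the REC". These are due within 15 days of the CI becoming aware. The section does not say what the event must be related to.

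**The concern.** The protocol names research procedures as a possible cause of SAEs and then provides no way to record that attribution. The individual REC report depends on the word related, and the only working definition of that word is the 13.2 scale. If the scale is followed literally, an event that a study procedure did cause gets the answer No and is not reported individually.

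The protocol itself anticipates sensitive moments in the research contact. Section 9.4 provides for children who show signs of not wanting to take part, for disclosures of risk, and for scores that suggest significant mental health difficulties. Harm from a procedure is therefore something the plan contemplates. Two people applying sections 13 to 13.3 to the same event could reasonably reach different reporting decisions.

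**Working it through.** No figure underlies this point, so the check is to set the passages side by side and follow an event through them.

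**Step 1: what each section covers.**

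| Section | Intervention | Research procedures |
|---|---|---|
| 13, scope | named | named |
| 13.2, question to the CI | named | absent |
| 13.2, Unrelated, Unlikely, Possible | named | absent |
| 13.2, Probable, Definite | causal relationship only, object not named | absent |
| 13.2, Yes/No column heading | named | absent |
| 13.3, individual REC report | related, object not stated | related, object not stated |

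Probable and Definite do not name the intervention in their own descriptions, but the column heading that governs them does. The scale as a whole therefore has one object.

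**Step 2: who is exposed to research procedures, and when.** Section 11.1 gives usual-practice schools the same assessment phases as intervention schools, with no ZF SEND until 12-month data collection is complete. Section 12.1 places recruitment, baseline assessment and randomisation in the summer term of 2021 and the start of delivery in September 2021. Each child is seen by a research assistant twice, at baseline and after the intervention. Because SAE collection starts at consent, the baseline session falls inside the reporting window.

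**Step 3: follow an SAE that a study procedure caused.**

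- *Usual-practice child, either assessment.* The child has not received ZF SEND, so the answer under 13.2 is Unrelated or Unlikely. Both map to No, and the individual REC report is not triggered.
- *Any child at baseline.* Delivery has not begun. The result is the same.
- *Intervention-arm child, at follow-up assessment, interview or recording.* Either the event is graded Unrelated or Unlikely and is not reported individually, or it is graded Possible or higher and the programme is credited with something the research contact caused. Neither result is right.

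**Step 4: what still happens to these events.** Under sections 13 and 13.3 each is reported to the study team within 24 hours, recorded, followed to resolution where possible, and assessed for seriousness. Each counts in the SAE rates by arm that go to the SSC. The only thing lost is the correct attribution and the individual report that depends on it.

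**The case against.** The strongest reply is that section 13.3 leaves related undefined and section 13 sets the scope for everything beneath it, so a careful reader would include research procedures. That reading is available, but 13.2 gives no grade on which to base it, and the Yes/No column points the other way. The ambiguity is reduced, not removed.

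A second reply is that oversight does not rest on the causality grade. This stands. A reader might infer that harm from a research procedure cannot reach the REC at all. The documents do not support that, because rates by arm go to the SSC and, if required, to the REC whatever the grade. That route is conditional and carries no attribution, so it does not replace an individual report, but it exists.

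A reader might also infer that the attribution rule is biased between arms, since only intervention-arm children can have an SAE graded as related. This does not hold either. An SAE in a child who has not received ZF SEND cannot have been caused by it, so not related to the intervention is the correct answer in usual practice and before delivery. The between-arm comparison in section 13 uses all SAEs, unfiltered by causality, and feasibility question 10 in section 5.3 judges harm on the outcome measures. No comparison in the protocol is distorted.

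Finally, section 6.1 rates the study as low risk, and the SAE definition in 13.1 sets a high threshold. Few, if any, questionnaire or interview sessions would be expected to lead to an SAE. That limits the practical weight of the point but does not reconcile the text.

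**Conclusion.** The point holds in a limited form. Sections 13, 13.2 and 13.3 do not fit together: one of the two causes named in the scope has no place on the causality scale, and an SAE from that cause would not qualify for the 15-day individual REC report under the scale as written. This applies in both arms and from consent onward.

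The number of events affected cannot be estimated from the protocol. Neither the share of children in usual practice nor the share of follow-up that precedes delivery measures it, because neither counts SAEs caused by research procedures. The conclusion assumes that 13.2 is applied as written and that related in 13.3 takes its meaning from that scale. If the study team already reads related in the wider sense of section 13, the practice may be sound and only the wording needs correcting. Causality definitions and ethics reporting criteria belong in the protocol, and this protocol fixes them, so the point is not one to leave to the analysis plan.

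**What to change.** Reconcile the three sections:

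1. In 13.2, add a second causality item, on the same five grades, for research procedures (assessments, interviews and recording). Complete both items for every SAE in both arms.
2. In 13.3, define related as possible, probable or definite on either item.
3. At the same time, replace the leftover references to a study medication with wording that suits an intervention session or a research procedure. This is editorial and changes no grade.

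The cost is one extra field on the SAE form and a few sentences of protocol text. No change to the design, sample size or analysis follows from it.

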13.3 Reporting procedures

Any queries concerning adverse event reporting should be directed to the Study Manager

All SAEs, whether expected or not, should be recorded on the relevant report form and followed up to resolution wherever possible. The CI (or delegated member of the SMG) should sign and date the SAE reporting form to acknowledge that he/she has performed the seriousness and causality

assessments. SAEs should be reported from time of signature of informed consent, throughout the treatment period.

An SAE form is not considered as complete unless the following details are provided:

- Full participant study number
- A Serious Adverse Event
- A completed assessment of the seriousness, and causality as performed by the CI (or another appropriately medically qualified doctor registered on the delegation log).
- Only reports of related and unexpected SAEs should be submitted to the REC. These should be sent within 15 days of the CI becoming aware of the event.

14 Statistical considerations

14.1 Randomisation

A sampling frame of potentially eligible schools will be drawn up and the order in which they will be approached will be determined (focussing on geographical areas nearest the study centres). Following this, schools will be allocated at random to information sheets describing a study where UP either does or does not offer delayed access to ZF SEND and approached consecutively. This randomisation process will be carried out using random permuted blocks. Following recruitment, enrolment of pupils, and baseline data collection, schools will be randomised to ZF SEND or UP using minimisation, with a random element set at 80% to maintain the integrity of the allocation process. Allocations will be balanced on the basis of school size (fewer than 100 pupils total vs 100 or more pupils - informed by special school sized reported by the DfE [35]), and study site (England/Scotland). An online password protected randomisation system will be carried out by a member of staff who will not be involved in recruitment, data collection, or analysis.

14.2 Blinding

Researchers who are blind to allocation will assess children's well-being by interviewing child participants according to the MAMS procedure (instances of accidental unblinding will be reported). Teachers, parents and child participants will not be blinded due to the nature of the intervention. The statistician will remain blind to allocation up until the point all analyses are completed.

14.3 Sample size

We aim to randomise 12 schools (8 in England and 4 in Scotland) in total and six per arm. Based on the pilot study, we estimate there will be one class/group per school and an average of eight children per class (and therefore eight children per school). We will therefore recruit 96 children in total (48 per arm). As this is a feasibility study, we seek to provide estimates of key parameters for a future trial and have not conducted a formal a priori power calculation. If two-thirds (66.7%) of

schools approached agree to take part (i.e. 12 out of 18 approached), the 95% CI around the percentage can be estimated within +/- 21.8% (i.e. 44.9% to 88.5%). Assuming that we obtain 12 month follow-up data for 75% of children, randomising 96 will allow the 95% CI for retention, to be estimated within +/- 8.7%.

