CRF	Case Report Form
CTR	Centre for Trials Research
СТU	Clinical Trials Unit
CU	Cardiff University
DM	Data Management
EQ-5D-Y	Euro-Qual-5 Dimensions Youth version
GCP	Good Clinical Practice
HE	Health Economics
IC	Informed consent
ICH	International Conference on Harmonization
ID	Intellectual Disability
IEC	Independent Ethics Committee
ISRCTN	International Standard Randomised Controlled Trial Number
MAMS	Me and my School
NASEN	National Association for Special Educational Needs
PI	Principal Investigator
PIS	Participant Information Sheet
QA	Quality Assurance
QC	Quality control
QL (QoL)	Quality of Life
QUALY	Quality Adjusted Life Year
R&D	Research and Development
RCT	Randomised Controlled Trial
REC	Research Ethics Committee
SAE	Serious Adverse Event
SOP	Standard Operating Procedure
TMF	Trial Master File
TMG	Trial Management Group
TSC	Trial Steering Committee
UoB	University of Birmingham
UP	Usual Practice
ZF	Zippy's Friends

1 Amendment History

The following amendments and/or administrative changes have been made to this protocol since the implementation of the first approved version.

Amendment No.	Protocol	Date issued	Summary of changes made since previous version
(specify	version no.		
substantial/non-			
substantial)			
			-

2 Synopsis

Short title	A randomised feasibility study of a school-based emotional literacy programme (Zippy's Friends) for children with intellectual disabilities.		
Acronym	ZF-SEND		
Development phase	Feasibility		
Funder and ref.	PHR Project NIHR 129064		
Study design	2 arm cluster-randomised feasibility study		
Study participants	Children attending special educational needs schools aged 9 – 11 years and their parents.		
Planned sample size	96 children (48 per arm).		
Planned number of sites	12 schools (8 in England and 4 in Scotland) in total comprising six per arm.		

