15.1 Main analysis

As this is a feasibility study, the analysis will be descriptive in nature. Continuous data will be reported as means and standard deviations, or medians and interquartile ranges, as appropriate. Categorical data will be reported as frequencies and proportions. All data will be reported both overall, per arm, and by setting type. Outcomes will be estimated with their associated 95% confidence intervals. No formal hypothesis testing will take place.

The study will be reported in accordance with the CONSORT extension for randomised pilot and feasibility studies.

Exploratory analysis of outcome measures to be used in the main trial will be based on the ITT principle, and will compare mean scale scores at 12-months between arms by fitting two-level linear regression models, with pupils nested within schools. The model will adjust for baseline scores, region (England or Scotland), and school size. Results will be reported as adjusted mean differences and 95% confidence intervals, focussing on effect sizes and their precision rather than p-values. Intra-cluster

correlation coefficients will be reported with associated 95% confidence intervals, with sources of variation explored using both quantitative and qualitative data.

We will also fit regression models to explore baseline factors associated with intervention receipt and retention in the study at the 12-month follow-up time points. Findings will be reported and may be used to inform study design modifications required in the main trial.

A detailed Statistical Analysis Plan will be written and signed off prior to undertaking any analysis.

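### The retention precision of ±8.7 points in Section 14.3 treats 96 pupils in 12 schools as independent, so it holds only if the retention ICC is practically zero

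*Protocol*

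**What the plan says.** Section 14.3 sets the size of the study by schools: "We aim to randomise 12 schools (8 in England and 4 in Scotland) in total and six per arm". With one class per school and about eight children per class, that makes 96 children, 48 per arm. The section says that no formal power calculation was done and gives two precision statements instead.

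- **School recruitment:** if 12 of 18 approached schools agree, ±21.8 points.
- **Child retention:** the planning value is 75% at 12 months, and the claim made for it is that "randomising 96 will allow the 95% CI for retention, to be estimated within +/- 8.7" per cent.

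No ICC, design effect or effective sample size accompanies the second statement.

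Elsewhere the protocol treats the data as clustered. The Synopsis calls the study a "2 arm cluster-randomised feasibility study". Section 14.1 randomises schools. Section 15.1 plans "two-level linear regression models, with pupils nested within schools" for the exploratory outcome comparisons and will report ICCs. Section 5.3 lists the ICC and the variation in cluster size for the SDQ among the parameters to be estimated (item 8). It also asks what proportion of schools, as well as of children and parents, is retained (item 6).

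**The concern.** A half-width computed as if the children were independent is too small when children in the same school tend to be retained or lost together. The protocol gives reasons to expect some of this. It foresees that schools may not be retained, and losing one average school would remove 8 of 96 children, or 8.3 points, at once. Under Section 12.1 teachers complete three questionnaires for each participating child, so with one class per school a single non-responding teacher could take a whole class's teacher data with them.

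Retention is among the primary feasibility outcomes in the Synopsis and Section 5.3, and this is the only precision statement attached to the 96 children. A reader of Section 14.3, including the funder or the Study Steering Committee, would expect more certainty about retention than the design is likely to give.

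**Working it through.** **Inputs from the protocol (Section 14.3):** retention p = 0.75; n = 96 children; 12 schools; mean cluster size m = 8; 95% confidence, z = 1.96.

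**Inputs not in the protocol, so assumed:** the ICC of retention, taken over 0.01 to 0.20; and the coefficient of variation (CV) of cluster size, taken as 0, with 0.5 as a sensitivity value. Section 6 mentions an average of 6–10 children per school but gives no CV.

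**Step 1: reproduce the stated figure.**

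Half-width = z × √(p(1 − p)/n) = 1.96 × √(0.75 × 0.25 / 96) = 0.0866, or 8.66 points. This rounds to the stated 8.7. Other independent-data intervals do not match: Wilson gives 8.5, Agresti–Coull 8.6, Clopper–Pearson 9.1 and a continuity-corrected interval 9.2. The stated figure is the simple binomial value, with a design effect of exactly 1.

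The companion figure reproduces in the same way: 1.96 × √((2/3)(1/3)/18) = 0.2178, or 21.8 points. There the school is the unit, so clustering of pupils does not arise and that figure stands.

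**Step 2: apply the design effect.**

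DE = 1 + (m − 1) × ICC = 1 + 7 × ICC; half-width = 8.66 × √DE; effective n = 96/DE.

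| Assumed ICC | DE | Effective n | Half-width (points) | Coverage of ±8.66 |
|---|---|---|---|---|
| 0.01 | 1.07 | 89.7 | 9.0 | 94% |
| 0.02 | 1.14 | 84.2 | 9.2 | – |
| 0.05 | 1.35 | 71.1 | 10.1 | 91% |
| 0.10 | 1.70 | 56.5 | 11.3 | 87% |
| 0.20 | 2.40 | 40.0 | 13.4 | 79% |

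Coverage is 2Φ(1.96/√DE) − 1; it was not computed for ICC 0.02.

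**Step 3: the ICC at which the stated figure fails.**

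The half-width stops rounding to 8.7 once it passes 8.75. That needs DE = (8.75/8.66)² ≈ 1.020 (using the unrounded 8.662), so ICC ≈ 0.020/7 ≈ 0.003.

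**Step 4: unequal schools.**

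With DE = 1 + ((1 + CV²)m − 1) × ICC and CV = 0.5, the half-width is 10.4 points at ICC 0.05 and 11.9 at ICC 0.10. Unequal cluster sizes add little to the equal-cluster values of 10.1 and 11.3.

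**The case against.** The arithmetic in Section 14.3 is correct for independent children; what is open to challenge is the unstated assumption of independence. Several stronger readings are tempting, and the protocol does not support them.

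- **That the trial will certainly miss ±8.7.** The protocol gives no ICC for retention. At 0.01 or 0.02 the half-width is 9.0 or 9.2 points, which is a small shift. The supportable statement is conditional: the figure fails unless the ICC is close to zero.
- **That the 96 children rest on this figure.** They do not. Section 14.3 obtains 96 as 12 schools times eight children, and correcting the half-width does not change that.
- **That a progression decision turns on this interval.** Section 6 refers to progression criteria, but the protocol states no retention threshold and ties nothing to a confidence limit. Section 4.1 leaves the conclusion on feasibility to the Study Steering Committee.
- **That the reported interval will be too narrow.** Section 14.3 is a planning statement. Section 15.1 does not say that pupil-level proportions will be analysed as independent, and it defers detail to a Statistical Analysis Plan that is not shown.
- **That the figure should also use a t distribution on 11 degrees of freedom.** That gives 9.7 points even at ICC 0, so it is a separate small-sample choice and not part of the missing design effect.

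All of this limits the weight of the point. None of it shows that clustering was allowed for in the stated figure.

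**Conclusion.** The point holds as a correction to a stated number. The ±8.7 in Section 14.3 has a design effect of 1 in a study that randomises schools and plans to model pupils within schools. It is right only if the ICC of retention is below about 0.003.

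Over assumed ICCs of 0.01 to 0.20, with eight children per school, the half-width is about 9 to 13 points. At the assumed 75% retention, the widest case runs from 61.6% to 88.4% (75 ± 13.4), against 66.3% to 83.7% as stated (75 ± 8.7). The size of the shortfall depends wholly on the ICC, which the protocol does not supply.

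Severity is moderate. The figure describes a primary feasibility outcome and is the only precision statement for the children, but the study has no power calculation, plans no formal hypothesis tests, and does not derive its size from this number.

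**What to change.** Replace the retention sentence in Section 14.3 with a cluster-adjusted one, for example: *allowing for clustering (8 pupils per school, assumed ICC 0.01 to 0.20), the 95% CI half-width for 75% retention is about 9 to 13 points.* State that the ICC range is an assumption, and give a source if the team has one.

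The school-recruitment figure of ±21.8 needs no change. How the retention interval is computed at reporting can be settled in the SAP; no change to Section 15.1 is needed for this point.

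The cost is one sentence and a less favourable stated precision. The number of schools and children stays the same.
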